1.2. Study Design

The present trial is designed as a phase 3b, randomized, double-blind, parallel-group, multicenter, comparison study in subjects of at least 18 years of age with moderate to severe plaque-type psoriasis. The study features the following structure and design:

Study Part 1: Screening through Week 28:

Part 1 consists of a screening phase lasting up to four weeks (+ 7 calendar days) prior to first administration of guselkumab (week 0), followed by a 28-week run-in period with visits and administration of 100 mg guselkumab at weeks 4, 12, and 20. In case of a PASI score = 0 at weeks 20 **and** 28, subjects are qualified to be randomized either to study group **2a** or **2b** of Study Part 2. In case of PASI score >0 at weeks 20 and/or 28, the subjects continue to receive guselkumab 100 mg q8w until week 60 (last administration at week 60 visit) with final study assessments at week 68 and final safety follow-up visit at week 72 (defined as study group **2c**).

Study Part 2: Week 28 through Week 68:

Subjects with a PASI score = 0 at weeks 20 **and** 28 are defined as SRe and randomly assigned to the following two treatment groups: **2a**) guselkumab 100 mg q8w or **2b**) guselkumab 100 mg q16w. In addition, subjects with disease duration \leq 2 years are equally distributed to either group by stratified randomization. Study visits of Study Part 2 are conducted every 8 weeks.

To blind the study, study treatment (guselkumab **or** Placebo) is administered q8w starting at week 28 until the end of study therapy (last administration in week 60). The q16w group receives Placebo at weeks 28, 44 and 60. Subjects losing control of disease, defined as PASI score >5 at any visit during Study Part 2 (ie, until week 60), enter the Re-treatment arm (group **2d**, see section Re-treatment below).

The assessment for the primary endpoint is made at week 68 for both study groups (**2a** and **2b**).

In case of PASI <3 at week 68, the subject does not receive any study medication and enters the drug withdrawal part (Study Part 3). In case of PASI \geq 3 at visit week 68 the subject enters the re-treatment arm **3c** (see section Re-treatment below).

In case of PASI score >0 at weeks 20 and/or 28 the subjects continue to receive guselkumab 100 mg q8w until week 60 (last administration of study treatment) with final study assessments at week 68 and final safety follow-up visit at week 72 (defined as study group **2c**).

Study Part 3: Week 68 through Week 220:

Subjects of group 2a and 2b with a PASI score <3 at week 68 enter Study Part 3 (in study groups **3a** and **3b**, respectively); they are withdrawn from the study medication and followed-up until week 220. Study visits of Study Part 3 are conducted every 12 weeks (ie, at weeks 80, 92, 104, 116, 128, 140, 152, 164, 176, 188, 200, and 212; \pm 14 days). In between the 12-weekly on-site visits, a telephone-visit 6 weeks (\pm 7 days) is done after each on-site visit (ie, telephone visits at weeks 74, 86, 98, 110, 122, 134, 146, 158, 170, 182, 194, and 206) to assess whether the subject notices a worsening of his/her psoriasis. If so, the subject must attend an on-site visit for efficacy assessment by the assessor as soon as possible but not later than 2 weeks after the phone call. For patients not starting re-treatment, the final visit takes place at week 220.

Re-treatment

Subjects losing control of disease, defined as PASI score >5 at any visit during Study Part 2 or 3 (ie, until week 220), enter the re-treatment-arms (**2d** or **3c**) with three guselkumab 100 mg administrations starting at that visit (= re-treatment-week 0, followed by administration at re-treatment-weeks 8 and 16).

[figure not shown]
If re-treatment is started at a visit which would usually not require all patient-reported outcomes needed at the first re-treatment visit, those patient-reported outcomes are obtained immediately after efficacy assessments (basis for re-treatment-decision) and prior to drug administration at that visit.

The final efficacy assessment for all subjects in the re-treatment arms takes place 24 weeks after loss of control, and study termination is 28 weeks after loss of control (final study visit/safety follow-up). At visit week 24 of the re-treatment, the investigator may continue actual treatment with commercially available guselkumab (ie, not supplied by Sponsor) to maintain a q8w interval. Due to the half-life of guselkumab, it is recommended not to start a new therapy during safety follow-up period (ie, 12 weeks after last dose). If the investigator feels strongly that an additional therapy is needed, this should be discussed with the Sponsor before initiation of the new therapy.

Subjects with fluctuating disease (ie, PASI score 3 to 5) at the week 68 visit also get the opportunity to enter the re-treatment-arm (**3c**).

The last chance to start re-treatment is the visit week 220 (ie, final efficacy assessment at week 244 with final study visit/safety follow-up at week 248).

A schematic diagram of the study design is provided below.

2. STATISTICAL HYPOTHESES

There is no statistical hypothesis for the Overall safety analysis.

3. SAMPLE SIZE DETERMINATION

The sample size estimation using the power approach was performed for the per-protocol analysis set for Study Part 2. No formal adjustment of the significance level was necessary.

When the sample size in each group is 112, a two-group large-sample normal approximation Wald Z-test of proportions with a one-sided 0.05 significance level will have 80% power to reject the null hypothesis that the guselkumab 100 mg q16w treatment is inferior to the guselkumab 100 mg q8w treatment (the difference in proportions, $P_{\text{guselkumab 100mg q16w}} - P_{\text{guselkumab 100mg q8w}}$, is $\leq -10\%$) in favor of the alternative hypothesis that the guselkumab 100 mg q16w treatment is non-inferior to the guselkumab 100 mg q8w treatment (the difference in proportions is $> -10\%$), assuming that the expected difference in proportions is 0 and the proportion in the guselkumab 100 mg q8w treatment group is 90% (nQuery Advisor® 7.0).

Considering the frequency of drop-out rates and protocol violations from past trials, it is assumed that a rate of about 20% randomized subjects will not be evaluable for the per-protocol analysis in Study Part 2. Therefore, 280 subjects (140 subjects per treatment group) are planned to be randomized in a ratio of 1:1 to meet the required sample size of 224 subjects (112 subjects per treatment group) for the per-protocol analysis.

Based on data from CNTO1959PSO3001 and CNTO1959PSO3002, it is anticipated that approximately 35% of enrolled subjects in Study Part 1 will be eligible for randomization at week 28 in Study Part 2. Thus, a total of 800 subjects should be enrolled in Study Part 1 to ensure that at least 280 subjects are eligible for randomization in Study Part 2. Accounting for a 10% drop-out rate of subjects ineligible for randomization at week 28 because of study discontinuation prior to week 28, it is therefore planned to enroll a total of 888 subjects in Study Part 1.

Note: Screenings and enrollments will be adjusted if necessary (without protocol amendment), to achieve 280 SRe at week 28. Ongoing subjects in Study Part I will continue to Part 2 if eligible, irrespective of whether or not 280 SRe are already randomized. Only screenings will be closed.

4. POPULATIONS (ANALYSIS SETS) FOR THE OVERALL SAFETY ANALYSIS

In the Overall safety analysis, the following analysis sets will be defined.

4.1. All Subjects Treated in Study Part 1

880 subjects started open-label guselkumab in Study Part 1 and received at least one dose (study group **1**). All 880 subjects are included in this analysis set to be evaluated for AEs in the study period from date of first dose (week 0) until the day before the date of the week 28 dose (start of randomized or open-label treatment within Study Part 2), or, in 58 subjects not starting Study Part 2, until the end of documentation.

4.2. All Subjects Treated in Study Part 2

From all 880 subjects who started open-label guselkumab in Study Part 1, 297 super-responders received randomized treatment in Study Part 2 (study groups **2a** and **2b**) and 525 non-super-responders continued open-label treatment (study group **2c**). So, 822 subjects are included in this analysis set and will be displayed separately to be evaluated for AEs in the study period from date

of the first verum dose (week 28 or week 36) until date of last verum dose (week 52 or week 60) in Study Part 2 plus 90 days (date of re-treatment and thereafter excluded, if at all).

4.3. All Subjects Randomized for Study Part 2

Among the 297 super-responders treated in Study Part 2 (study groups **2a** and **2b**), 148 were randomized to guselkumab q8w and 149 to guselkumab q16w. The 297 subjects included in this analysis set will be evaluated and displayed separately for AEs in the study period from date of randomization (week 28) until date of last verum dose (week 52 or week 60) in Part 2 plus 90 days (date of re-treatment and thereafter excluded, if at all).

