6. DOSAGE AND ADMINISTRATION

A guselkumab-prefilled syringe assembled with the UltraSafe Plus™ Passive Needle Guard (PFS-U) device, designed to deliver a single, fixed dose of 100 mg and a matched PFS-U containing Placebo will be used. Products will be labeled in a blinded manner; it will not be possible to differentiate between active and Placebo-prefilled syringes.

For **Study Part 1** all enrolled subjects will receive one injection of guselkumab according to the TES, ie at weeks 0, 4, 12, and 20.

Subjects with a PASI score=0 at weeks 20 and 28 are qualified for randomization in Study Part 2. In case of PASI score >0 at weeks 20 or/and 28, subjects will continue to get guselkumab 100 mg q8w with last administration in week 60.

Randomized subjects of **Study Part 2** (study group 2a and 2b) will receive one injection of either guselkumab or matching Placebo solution for injection (ie, identical to guselkumab in color, smell, and shape) according to the following schemes:

- Study group 2a: guselkumab 100 mg q8w, ie at weeks 28/36/44/52/60
- Study group 2b: guselkumab 100 mg q16w, ie guselkumab at weeks 36 and 52; Placebo at weeks 28/44/60 (guselkumab and placebo will be provided blinded, IWRS will assure correct assignment).

Subjects of groups 2a and 2b with a PASI score <3 at week 68 are qualified for entering **Study Part 3** and will be withdrawn from the study medication.

Subjects of groups 2a,2b, 3a and 3b losing control of disease, defined as PASI score >5 at any visit of Study Parts 2 or 3 (ie, until week 220), will enter the re-treatment arm with guselkumab 100 mg q8w for further 3 administrations (starting at that visit = re-treatment week 0, followed by administration at re-treatment-weeks 8 and 16). The final efficacy assessment for all subjects in the re-treatment arms will take place 24 weeks after loss of control and study termination will be 28 weeks after loss of control (final study visit). Subjects with fluctuating disease (ie, PASI score 3 to 5) or PASI >5 (subjects losing control of disease) at week 68 will also get the opportunity to enter the re-treatment-arm.

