In addition to above analyses, safety aspects need to be evaluated using the adverse event (AE) data from the entire study period. This current SAP describes the statistical analyses planned to be performed for this purpose and should be read in conjunction with the CSP and the electronic Case Report Form (eCRF).

This plan is the core document for all statistical programming planned for the Overall safety analysis of study protocol no. CNTO1959PSO3012. The statistical analysis will focus on the comparison of adverse event data in various subgroups.

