5.4.1. Adverse Events

The verbatim terms used in the eCRF by investigators to describe adverse events (AEs) are coded using the Medical Dictionary for Regulatory Activities (MedDRA). For analysis, AEs will be summarized by MedDRA system organ class (SOC) and Preferred Terms (PT) for each analysis group and overall.

For each analysis set, a separate time period will be considered for analysis:

Analysis set	Time period to be analyzed	Excluded time period
All subjects treated in Study Part 1 (N = 880)	Date of first dose (week 0) until study end	Date of week 28 dose and thereafter
All subjects treated in Study Part 2 (N = 822) #	Date of first verum dose (week 28 or week 36) until Date of last verum dose (week 52 or week 60) in Study Part 2 plus 90 days	Date of re-treatment and thereafter
All subjects randomized for Study Part 2 (N = 297) §	Date of randomization (week 28) until Date of last verum dose (week 52 or week 60) in Study Part 2 plus 90 days	Date of re-treatment and thereafter
All subjects with a Withdrawal phase longer than 90 days (N < 273)	91 st day after last verum dose in Study Part 2 until the day before re-	Date of re-treatment and thereafter

Analysis set	Time period to be analyzed	Excluded time period
	treatment is started (or study end if no re-treatment was started)	
All subjects who started re-treatment (N = 236)	Date of first re-treatment dose (week R0) until study end	None

In this analysis, subjects will be evaluated as well by analysis groups (super responders and non-super-responders).

§ In this analysis, subjects will be evaluated only by analysis groups (treated q8w and treated q16w).

If the AE onset date is recorded partially only or is completely missing, then the event will be considered for analysis unless it is known to be prior to the respective time period based on partial onset date or resolution date. Rules to impute a partial or missing onset date are presented in Section 5.1.5. In case a subject missed the week 68 visit, the date of the week 68 visit will be estimated as 8 weeks (56 days) after the week 60 visit.

For each AE, the number and percentage of subjects who experience at least one occurrence of the given event (SOC, PT) will be summarized by analysis group and overall. Summary tabulation will also provide the number of events, if applicable.

Summary tables will be provided – separately for each analysis set – for:

- AEs
- AEs by highest relationship to study agent
- AEs by worst severity
- Infections

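### Overall safety SAP: set 4.2 starts q16w super-responders at week 36 instead of week 28, so its super-responder column omits up to eight weeks of AEs that are tabulated only in set 4.3

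*SAP*

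**What the plan says.** All references are to the overall safety SAP unless stated.

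- **Set 4.1 (treated in Part 1, N = 880).** For subjects who continue, AEs count "until the day before the date of the week 28 dose". Section 4.1 explains that dose as the "start of randomized or open-label treatment within Study Part 2", so it includes a placebo syringe. The table in 5.4.1 agrees and excludes "Date of week 28 dose and thereafter".
- **Set 4.2 (treated in Part 2, N = 822).** AEs count from the date "of the first verum dose (week 28 or week 36) until date of last verum dose" in Part 2, plus 90 days. The table in 5.4.1 gives the same start. A footnote to that table says this set is also shown by super-responders and non-super-responders.
- **Set 4.3 (randomized, N = 297).** AEs count from randomization at week 28 in both arms, to the same end as set 4.2. It is shown only as q8w against q16w.
- **Dosing.** Section 1.2 states: "The q16w group receives Placebo at weeks 28, 44 and 60". Protocol section 6 gives group 2b "guselkumab at weeks 36 and 52; Placebo at weeks 28/44/60". The last Part 1 dose is at week 20.
- **Output.** Section 5.4.1 asks for numbers and percentages of subjects with events. Appendix 7 (section 6.7) leaves exposure out of this analysis.

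**The concern.** For q8w subjects and non-super-responders, set 4.2 begins the day after set 4.1 ends. For q16w subjects it begins eight weeks later. An AE, SAE, infection or reaction to the week 28 injection that starts in those eight weeks in a q16w subject is in neither set.

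What is at stake is the super-responder versus non-super-responder table in set 4.2. Half of the super-responders (149 of 297) are observed from week 36, while everyone they are compared with is observed from week 28. All 297 stay in the denominator and no rate per exposure time is planned. The shorter window can therefore lower the super-responder percentages or leave them unchanged, but cannot raise them. The overall column of the same table is affected in the same way.

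**Working it through.** **Counts stated in sections 4.1 to 4.3.** 297 + 525 = 822; 880 − 822 = 58 not starting Part 2; 148 + 149 = 297. All agree with the SAP.

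**Windows.** Put week *w* on study day 7*w* + 1, with on-schedule visits. Week 28 is day 197, week 36 day 253, week 52 day 365 and week 60 day 421. The window end is last active dose + 90 days: 365 + 90 = 455 for q16w and 421 + 90 = 511 for q8w.

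| Set and group | Nominal days | Length (days) |
|---|---|---|
| 4.1, subjects who continue | 1–196 | 196 |
| 4.2, q8w | 197–511 | 315 |
| 4.2, q16w | 253–455 | 203 |
| 4.3, q8w | 197–511 | 315 |
| 4.3, q16w | 197–455 | 259 |

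**Gap between 4.1 and 4.2.**
- q8w and non-super-responders: 197 − 196 − 1 = 0 days.
- q16w: 253 − 196 − 1 = 56 days (days 197–252).

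**Is the gap covered elsewhere?** Set 4.3 for q16w starts on day 197. On the nominal schedule, 4.1 and 4.3 are contiguous for super-responders, and 4.1 and 4.2 are contiguous for non-super-responders.

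**Size, if every q16w subject stays to week 36.**
- 149 × 56 = 8,344 subject-days; 8,344 / 365.25 = 22.8 subject-years.
- Per q16w subject, as a share of the window from week 28: 56 / 259 = 21.6%.
- Super-responder time from week 28: 148 × 315 + 149 × 259 = 46,620 + 38,591 = 85,211 subject-days. Share omitted: 8,344 / 85,211 = 9.8%.

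**Consistency within set 4.2.** The omitted interval starts with a placebo injection eight weeks after an active dose (week 20 to week 28) and ends at the next active dose (week 36). Weeks 44 to 52 have the same structure: active at 36, placebo at 44, active at 52. That interval, days 309–364, lies inside the q16w window and is counted. So is the week 60 placebo injection (day 421, before day 455).

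**After moving the start to week 28.** The q16w window becomes 203 + 56 = 259 days and the gap becomes 0. The difference from q8w falls from 315 − 203 = 112 days to 315 − 259 = 56 days. The remaining 56 days come entirely from the end date (511 − 455).

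**The case against.** The strongest reply has four parts.

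- **The AEs are in the analysis.** Section 5.4 applies the analyses to all five sets, and set 4.3 tabulates these events in the q16w column. This stands. A reader might infer that the events vanish, or that the introduction's statement that "safety aspects need to be evaluated using the adverse event (AE) data from the entire study period" is contradicted. The documents do not support that, because set 4.3 takes over from set 4.1 for super-responders.
- **The start may be deliberate.** Both possible weeks are written out in the text and in the table, next to a second set that starts at randomization. An analysis based on active drug is a legitimate aim. But section 4.2 gives no reason, and a rule meant to leave out placebo intervals would also leave out weeks 44 to 52.
- **The fix does not equalise the comparison.** Correct: the earlier q16w end date remains.
- **The stakes are low.** The analysis was not planned in the protocol, has no hypothesis and is purely descriptive. Part 2 safety was also analysed under its own SAP, which is not among the documents here. This limits the weight of the point but does not remove it.

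A reader might also argue that part of the gap is on-treatment time by the SAP's own 90-day rule: week 20 is day 141, 141 + 90 = 231, and days 197–231 are 35 of the 56 days. The SAP states the 90 days only for the last active dose in Part 2, and set 4.1 has no such tail. That argument is therefore an inference and is not used here.

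**Conclusion.** The point holds for set 4.2 only. AEs of q16w subjects from the week 28 injection to the day before the week 36 dose are missing from sets 4.1 and 4.2 and appear only in set 4.3, which has no non-super-responder column. The bias in the super-responder column has a known direction, downward or nil. Its size in events cannot be derived from the documents.

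The subject-day figures are upper bounds. They assume on-schedule visits, no discontinuation before week 36 and no truncation by re-treatment; section 4.5 reports three subjects re-treated during Part 2. An AE with a partial or missing onset date may already enter set 4.2, because 5.4.1 counts it unless it is known to precede the period.

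This should be corrected because it is a one-sided omission in a safety comparison and is cheap to repair. It does not touch the primary analysis or the q8w versus q16w safety tables in set 4.3.

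**What to change.** In section 4.2 and in the table in 5.4.1, start the set 4.2 window at the date of the week 28 study injection, active or placebo, for all 822 subjects. Set 4.2 then begins the day after set 4.1 ends and has the same nominal start as set 4.3. It also gives a start date to any q16w subject who stopped before week 36; the documents do not say whether there are any.

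Add two footnotes to the set 4.2 tables:

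- The q16w window ends 90 days after week 52 and the q8w window 90 days after week 60, so follow-up remains unequal.
- AEs with partial or missing onset dates may be counted in more than one set under 5.4.1.

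If the sponsor prefers to keep the active-dose start, the SAP should give the reason and note in the tables that q16w AEs from week 28 to week 36 are found in set 4.3.

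The cost is one date definition, the footnotes and a re-run of the set 4.2 tables. No new data are needed.

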6.7. Appendix 7 Intervention Compliance

Exposure to study agent and study compliance are not part of this analysis..

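### Overall safety SAP, set 4.3: q8w and q16w adverse event percentages are shown side by side over nominal windows of 314 and 258 days, with no patient-time rate planned

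*SAP*

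**What the plan says.** The overall safety SAP gives the 297 randomised super-responders (148 q8w, 149 q16w) a single window rule in Section 4.3: AEs are counted "from date of randomization (week 28) until date of last verum dose (week 52 or week 60) in Part 2 plus 90 days", with time from any re-treatment onward excluded. The period table in Section 5.4.1 repeats the rule.

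The two end weeks belong to different arms. Protocol Section 6 gives group 2a active drug at weeks 28, 36, 44, 52 and 60, and group 2b "guselkumab at weeks 36 and 52; Placebo at weeks 28/44/60". The SAP's own design summary (Section 1.2) agrees: "The q16w group receives Placebo at weeks 28, 44 and 60".

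The table footnote for this set begins "In this analysis, subjects will be evaluated only by analysis groups (treated q8w and treated q16w", so regimen is the only grouping. The planned measure is: "For each AE, the number and percentage of subjects who experience at least one occurrence of the given event (SOC, PT) will be summarized". Event counts are added where applicable. Section 5.1 likewise plans counts and proportions for categorical data. No rate per unit of time appears anywhere in the text.

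The Introduction states the purpose: "The statistical analysis will focus on the comparison of adverse event data in various subgroups".

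**The concern.** A percentage of subjects with at least one event depends on how long the subjects are watched. Here the two randomised arms are watched for different nominal lengths because the window is tied to the last active dose. The q16w schedule reaches that dose eight weeks earlier.

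The direction is predictable. With identical event rates, q16w, the extended-interval regimen under test, would show lower percentages and fewer events. The analysis has no tests or confidence intervals, so the displayed figures are the whole result. A reader comparing the two columns could take a difference in window length for a difference in safety.

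**Working it through.** **Inputs.** Window rule and arm sizes: overall safety SAP 4.3. Dosing weeks: Protocol Section 6. Target study days: visit-window table in the Part 3 SAP, Section 5.1.1.

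**Reproducing stated figures.** The documents do not give the window lengths in days. The nearest stated figures are the target days. Target day = 7 × week + 1 gives 197 (week 28), 365 (week 52), 421 (week 60) and 477 (week 68), all as printed. Arm sizes: 148 + 149 = 297, as printed.

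**Window length** = (last active week − 28) × 7 + 90.
- q8w: (60 − 28) × 7 + 90 = 314 days, ending on study day 421 + 90 = 511.
- q16w: (52 − 28) × 7 + 90 = 258 days, ending on study day 365 + 90 = 455.
- Difference 56 days; 1 − 258/314 = 17.8% shorter.

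The q16w window thus closes 477 − 455 = 22 days before the week 68 target day, while the q8w window runs past it. An AE starting on day 460 counts in set 4.3 for a q8w subject but not for a q16w subject.

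**Nominal patient-years** (full follow-up, no cut at re-treatment).
- q8w: 148 × 314 / 365.25 = 127.2.
- q16w: 149 × 258 / 365.25 = 105.2.
- Ratio 0.827, so equal event rates give about 17% fewer q16w events.

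**Effect on percentages.** The documents give no AE rates, so the q8w percentages below are assumed over a range. With the same constant hazard in both arms, p16 = 1 − (1 − p8)^(258/314). The standard error (SE) of the difference is √[p8(1 − p8)/148 + p16(1 − p16)/149].

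| q8w (assumed) | q16w shown | Shift (points) | SE (points) | Shift/SE |
|---|---|---|---|---|
| 5% | 4.1% | 0.9 | 2.4 | 0.36 |
| 10% | 8.3% | 1.7 | 3.3 | 0.51 |
| 30% | 25.4% | 4.6 | 5.2 | 0.89 |
| 50% | 43.4% | 6.6 | 5.8 | 1.14 |
| 70% | 62.8% | 7.2 | 5.5 | 1.31 |

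For individual event rows at 5–10% the shift is well inside sampling noise. For a summary row at 50–70% it slightly exceeds one SE.

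**Set 4.2.** This set compares super-responders with non-super-responders, and its window starts at the first active dose. For q16w subjects that is (52 − 36) × 7 + 90 = 202 days, so pooled super-responders average (148 × 314 + 149 × 202)/297 = 257.8 days. The stated rule gives non-super-responders 314 days. Their last scheduled contact comes slightly earlier, since they finish "with final study assessments at week 68 and final safety follow-up visit at week 72", which is (72 − 28) × 7 = 308 days. These windows differ too, but the groups are not randomised.

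**The case against.** The strongest reply is that an equal-window comparison of the arms already exists. The Introduction to the overall safety SAP describes a separate Part 2 analysis whose safety evaluation runs from week 28 to week 68, nominally 280 days in both arms. Set 4.3 is an additional view, introduced by this SAP (Section 6.2), with no hypothesis (Section 2) and no inferential statistics (Section 5). This stands, and it limits the weight of the point. It does not correct the tables that this SAP will itself produce.

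Tying the window to active drug also looks deliberate and coherent: set 4.4 starts on the 91st day after the last active dose. A reader might infer that later q16w events are lost. They are not: in subjects who qualify for set 4.4 they are counted there. The window rule itself is not at fault.

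Three other stronger readings are not supported:
- That the plan conceals which arm has which window. The assignment is not spelled out beside the rule, but it follows from the placebo weeks in Section 1.2.
- That Section 6.7 rules out a time denominator by saying "Exposure to study agent and study compliance are not part of this analysis". That sentence sits under intervention compliance and concerns dosing, not AE observation time. The absence of a rate rests on Sections 5.1 and 5.4.1.
- That the safety comparison of the two regimens in this trial is biased as a whole. The Part 2 analysis shows otherwise.

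It could also be said that q8w events after week 68 are barely captured, which would narrow the gap. The documents point the other way: 273 of the 297 entered the withdrawal phase (Section 4.4), where AE collection continues (Protocol 9.6).

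Table shells for this SAP were not among the documents, so a rate planned only there cannot be excluded.

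**Conclusion.** The point holds for set 4.3. Followed as written, the plan displays the randomised arms over nominal windows of 314 and 258 days with no time denominator. At equal event rates this lowers the q16w figures: about 17% fewer events, and roughly 1 to 7 percentage points for assumed q8w percentages between 5% and 70%.

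The window lengths follow directly from the documents. The shifts in percentages rest on assumed AE frequencies, equal constant hazards, full follow-up and no cut at re-treatment. Early discontinuation and re-treatment shorten individual windows, which is a reason to use actual rather than nominal time.

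This is a minor-to-moderate reporting bias in a supplementary descriptive analysis. It touches neither the primary endpoint nor any test or decision rule.

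**What to change.** Keep the analysis sets, their windows and the planned percentages. For set 4.3, add to Section 5.4.1 and its tables:
- subjects with an event per 100 patient-years, with each subject's actual time in the window counted to the first event;
- events per 100 patient-years, with each subject's full actual time in the window;
- a footnote giving the nominal window by arm: q8w 314 days, q16w 258 days.

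The same two rates may be added for set 4.2, with a note that super-responders and non-super-responders are not randomised groups. Rates there would remove the effect of window length but would not make the contrast a fair comparison.

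The cost is small: person-time variables derived from dates already needed to apply the windows, two extra columns and a footnote. No new data are required.
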